6.1.1 Medical Devices

1. Medical device (not manufactured by or for Thirty Respiratory Limited) provided for use in this study will be an FDA-approved and CE-marked vibrating mesh nebulizer.
2. Instructions for medical device use will be provided in the User Manual.

6.1.2 Device Training

Training will be provided to ensure all study staff are familiar with the device, including mixing the solutions, adding the admixture to the device and cleaning the device.

6.2 Preparation, Handling, Storage, and Accountability

6.2.1 Preparation of Study Intervention Product

RESP301 is prepared at bedside by mixing two sterile 3 mL solutions (one of NaNO₂/mannitol and one of citric acid buffered to pH 5.4). The solution is to be nebulized immediately or within 5 minutes post mixing as per the instructions given in the SoA (Table 1-1) and, for the first 10 participants, as in Section 6.1 above (staggered dosing). The first administration of study intervention should be provided under clinical supervision.

RESP301 is mixed in the nebulizer chamber before use following the steps below (see Table 6-2 for details of composition):

1. First the vial marked A (NaNO₂ and mannitol) is opened and its contents are poured into the nebulizer chamber.
2. Next, the vial marked B (citric acid) is opened and its contents are poured into the nebulizer chamber.
3. The nebulizer lid should be closed, and the nebulizer should be swirled gently for a few seconds to mix the two solutions. The nebulizer should not be inverted.

The inhalation of the medication should start within 5 minutes of mixing the solutions and the inhalation process should be complete within 20 minutes of starting inhalation.

This combined mildly acidified nitrite solution (6 mL) is inhaled through the mouth using a vibrating mesh nebulizer under the direction of the clinical team. The purpose of the acidified nitrite aerosol is to deliver NO to the participant. The delivered dose of RESP301, assessed via simulated tidal breathing is estimated to be ~40% of the masses listed below; it should be noted that delivered dose can be further affected by participant's breathing pattern and inspiratory capacity and so inter- and intra-participant variation in actual doses of these ingredients may vary, given the acute nature and high disease burden in this proposed clinical setting.

Table 6-2 Composition of Drug Product, Diluent and Admixture

	Material	Function	Quantity per vial
Drug Product	Sodium Nitrite	Drug Substance	62.10 mg
	Mannitol	Excipient	54.66 mg
	Sterile water for injection	Diluent	
	Total Volume		3.0 mL
Diluent	Citric Acid	Diluent	115.28 mg
	Sterile water for injection	Diluent	
	Total Volume		3.0 mL
Acidified Drug Product Mixture (RESP301)	Sodium Nitrite	Drug Substance	62.10 mg
	Mannitol	Excipient	54.66 mg
	Citric Acid	Diluent	115.28 mg
	Sterile water for injection	Diluent	
	Total Volume		6.0 mL

6.2.2 Storage and Accountability of Study Intervention

The Investigator or designee must document whether appropriate temperature conditions (<25°C) have been maintained during storage for all study intervention received and any discrepancies are reported and resolved before use of the study intervention. Temperature excursions are permitted up to 30°C for no longer than 1 hour. Such a temperature excursion must be recorded, however the study intervention can be safely administered to participants.

Only participants enrolled in the study may receive study intervention and only authorized site staff may supply or administer study intervention. All study interventions must be stored in a secure, environmentally controlled, and monitored (manual or automated) area in accordance with the labeled storage conditions with access limited to the Investigator and authorized site staff.

The investigator, institution, or the head of the medical institution (where applicable) is responsible for study intervention accountability, reconciliation, and record maintenance (e.g., receipt, reconciliation, and final disposition records).

Further guidance and information for the final disposition of unused study intervention are provided in the Investigator Manual.

6.3 Measures to Minimize Bias: Randomization and Blinding

This is an open-label study; however, the specific intervention to be taken by a participant will be assigned using an interactive voice response system (IVRS)/interactive web response system (IWRS). The site will contact the IVRS/IWRS prior to the start of study intervention administration for each participant. The site will record the intervention assignment on the applicable case report form (CRF), if required.

Potential bias will be reduced using a central stratified randomization to assign participants into one of the study treatment arms, RESP301+SOC or SOC (control), with a randomization ratio of 2:1. Participants will be stratified by country and presence of risk factors for severe outcomes of COVID-19, based on comorbidities and age as follows:

1. Age >65 years
2. Ongoing or currently treated diabetes mellitus
3. Ongoing or currently treated hypertension
4. Ongoing or currently treated cardiovascular disease
5. Ongoing or currently treated chronic lung disease
6. Cancer history of less than 3 years, basal cell skin carcinoma excluded
7. Ongoing or currently treated chronic kidney disease

Participants will be stratified as no risk factor (none of the above criteria), one risk factor (one single of the above) or high-risk factor (2 or more of the above).

6.4 Study Intervention Compliance

Participants will receive study intervention directly from the Investigator or designee, under clinical supervision. The date and time of each inhalation will be recorded in the source documents and recorded in the CRF. The study participant identification will be confirmed at the time of dosing by a member of the study site staff other than the person administering the study intervention.

6.5 Concomitant Therapy

During the study, participants will receive institutional SOC for the treatment of COVID-19.

Any medication or vaccine (including over-the-counter or prescription medicines, vitamins, and/or herbal supplements) that the participant is receiving at the time of enrollment or receives during the study must be recorded along with:

- Reason for use
- Dates of administration including start and end dates
- Dosage information including dose and frequency and route

The Medical Monitor should be contacted if there are any questions regarding concomitant or prior therapy.

6.5.1 Potential Drug Interactions

Investigators should be aware of the potential interaction between NO generated by RESP301 and that generated from NO donor agents, such as prilocaine, sodium nitroprusside, and nitroglycerine, that may increase the risk of developing methemoglobinemia.

6.5.2 Rescue Medication

For participants treated before completion of the first safety review by the IDMC (Section 9.6), at the time of RESP301 treatment, a ready-to-use nebulization of a bronchodilator (short acting beta agonist such as salbutamol/albuterol according to investigational site standard practice for acute bronchospasm) may be administered to participants in case of bronchospasm.

After reviewing safety data, the IDMC will decide whether the availability of rescue bronchodilator at the time of RESP301 treatment is still required.

Although the use of rescue medications is allowable for the first 10 participants, the use of rescue medication should be delayed, if possible, for at least 2 minutes following each administration of study intervention. The date and time of rescue medication administration as well as the name of the rescue medication must be recorded.

6.6 Intervention After the End of the Study

After the end of the study, participants may continue their SOC (if any). Study intervention for COVID-19 will not continue beyond this study.

7 Discontinuation of Study Intervention and Participant Discontinuation

7.1 Permanent Discontinuation of Study Intervention

It may be necessary for a participant to permanently discontinue (definitive discontinuation) study intervention. If study intervention is definitively discontinued, the participant will remain in the study to be evaluated for the Day 14 and Day 28 safety follow-ups. See the SoA (Table 1-1) for data to be collected at the time of discontinuation of study intervention and follow-up and for any further evaluations that need to be completed.

Study intervention will be permanently discontinued prior to 10 days if the participant:

- Improves to level 1 or 2 of the modified WHO ordinal scale;
- Progresses to a level > 4 of the modified WHO ordinal scale.

Additionally, study intervention should be permanently discontinued in the following circumstances:

1. Discontinuation of study intervention for abnormal liver tests should be considered if the Investigator believes that it is in best interest of the participant. The development of alanine aminotransferase (ALT) $\geq 3 \times$ ULN and bilirubin $\geq 2 \times$ ULN or ALT $\geq 3 \times$ ULN and international normalized ratio (INR) > 1.5 , if INR is measured, which may indicate severe liver injury (according to Hy's Law), must be reported as an SAE and the study intervention discontinued.
2. If, as part of normal clinical follow-up, a clinically significant change in ECG is identified, the Investigators should exercise their clinical judgement to decide whether continuing study intervention administration is in the best interest of safety of the participant.
3. AE/SAE if the Investigator believes that it is in best interest of the participant, including the following:
 - Development of significant bronchospasm * or worsening of cough that is not tolerated by the participant and leads to immediate discontinuation of the nebulization.
 - Progressive COVID-19 requiring initiation of invasive ventilation or high flow oxygen.
 - Development of mHb level above 3%.

- Inability to safely continue receiving study intervention due to compromised respiratory status while off supplemental oxygen and receiving nebulized therapy (manifest by drop in SpO₂, increased respiratory rate or clinical other findings).

Refer to the SoA (Table 1-1) for data to be collected at the time of study intervention discontinuation and follow-up and for any further evaluations that need to be completed.

** Inhaled citric acid and inhaled mannitol provoke bronchospasm in patients with bronchial hyperresponsiveness in a dose dependent pattern. Although the concentrations of mannitol and citric acid are below the provocative dose and concentration inducing bronchospasm, there is a theoretical risk that a participant may develop acute bronchospasm during the use of RESP301. Participants should therefore be monitored during RESP301 administration. In case of clinical intolerance or saturation decrease, nebulization should be immediately discontinued (see Section 7.2). Further clarification of the differences in signs and symptoms for acute bronchospasm and COVID-19 progression are provided in Table 7-1.*

Table 7-1 **Differences in Signs and Symptoms for Acute Bronchospasm and COVID-19 Progression**

	Acute bronchospasm related to inhaled bronchial irritant	Progression of COVID-19 lung disease to acute respiratory failure
Mechanism	Acute contraction of bronchial muscles resulting in bronchial obstruction resulting in increased ventilatory load	Cytokine storm resulting in alveolar damage resulting in gas transfer impairment
Onset	Within minutes (<15 minutes) following inhalation (no late phase since it is not an allergic IgE mediated reaction)	Within hours or days and not related to nebulization
Clinical auscultatory signs	Wheezing (almost all cases)	Bilateral rales (inconstant)
Patient history	Asthma or respiratory allergy	Age > 65 years, increased BMI, high blood pressure, cardiac diseases, etc.
Reversibility with inhaled beta mimetics	Within minutes	No

Abbreviations: BMI=body mass index; IgE=immunoglobulin E.

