6.1 Study Intervention Administered

[figure not shown]
Table 6-1 Study Intervention(s) Administered

Study Treatment	RESP301 + SOC
Intervention Name:	RESP301
Type:	Drug
Dosage Formulation:	Admixture for inhalation
Unit Dose Strength(s):	Delivered dose (62 mg) sodium nitrite (NaNO ₂) (6 mL of NO-generating admixture of 150 mM NaNO ₂ , 50 mM mannitol and 100 mM citric acid)
Dosage Level(s):	One 6 mL-inhalation TID (every 8 hours) with at least 6 hours between 2 consecutive doses.
Route of Administration:	Inhalation
IMP and NIMP:	IMP
Sourcing:	RESP301 provided centrally by the Sponsor.
Dosing Instructions:	A vibrating mesh nebulizer will be used to administer the RESP301, under the direction of the study physician. Treatment is to commence within 5 minutes of RESP301 preparation. For the first 10 participants (and enrolment up to completion of the first IDMC safety review) RESP301 will be administered by intermittent inhalation to monitor tolerability and response to RESP301. After reviewing safety data, the IDMC will decide whether the intermittent inhalation of RESP301 can be replaced by a continuous inhalation. Before initiating each RESP301 inhalation, supplemental oxygen, if being used, will be interrupted for a few minutes until SpO ₂ levels are stable. Depending on the extent of SpO ₂ decrease, the RESP301 inhalation may be initiated or supplemental oxygen may be resumed at the discretion of the investigator. After treatment initiation, in case of SpO ₂ decrease, RESP301 inhalation may be paused and supplemental oxygen resumed. If the participant is unable to tolerate nebulization without supplemental oxygen, nasal oxygen may be administered during nebulization.
Packaging and Labeling:	Study intervention will be provided as two separate vials: NaNO ₂ /mannitol (3 mL) and citric acid buffered to pH 5.4 (3 mL), which will be labeled as required per country requirement.

Staggered dosing approach for the first 10 participants:

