7.2 Temporary Discontinuation of Study Intervention

Brief temporary discontinuation of study intervention is permitted during the study, providing inhalation of study intervention is completed within 20 minutes.

Study intervention should be temporarily discontinued in the following circumstance:

1. Clinical intolerance to nebulization.

An individual administration of study treatment will be stopped, and supplemental oxygen if applicable resumed, if threshold limits of SpO₂ 89% or heart rate 120 beats/min (or as indicated by the Investigator) are exceeded (see Sections 4.2 and 8.1.2).

The participant may continue with subsequent doses if the Investigator judges that the benefit / risk ratio remains positive. In this case, the instruction to continue should be duly recorded in the participant's hospital file and the subsequent nebulization should be closely monitored.

Refer to Section 6.1 for information on staggered dosing in the first 10 participants.

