8.1 Efficacy Assessments

8.1.1 Modified WHO Ordinal Scale

A modified WHO ordinal scale will be used for consistency with the recent study of lopinavir-ritonavir in adults hospitalized with severe COVID-19 (Cao et al, 2020), to record the participant's status at the time of assessment. The modified WHO ordinal scale includes the following levels:

1. Not hospitalized, no limitations on activities;
2. Not hospitalized, limitation on activities;
3. Hospitalized, not requiring supplemental oxygen;

4. Hospitalized, requiring supplemental oxygen;
5. Hospitalized, on non-invasive ventilation or high-flow oxygen devices;
6. Hospitalized, on invasive mechanical ventilation or extra corporeal membrane oxygenation (ECMO);
7. Death.

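### Protocol Section 7.1 makes respiratory progression a mandatory stop in one list and a narrower, discretionary stop in the next, and leaves the force of its mHb limit unclear

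*Protocol*

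**What the plan says.** All references are to the amended protocol, which admits WHO level 3 and level 4 participants.

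- **Section 7.1, first list.** Study treatment is to be stopped for good before Day 10 if the participant "Progresses to a level > 4 of the modified WHO ordinal scale". Sections 1.1 and 4.1 carry the same rule. None of the three places makes it subject to Investigator judgement.
- **Section 8.1.1.** Level 5 is "Hospitalized, on non-invasive ventilation or high-flow oxygen devices". Level 6 includes invasive mechanical ventilation, and level 7 is death.
- **Section 7.1, second list.** It opens: "Additionally, study intervention should be permanently discontinued in the following circumstances". Item 3 of that list then begins: "AE/SAE if the Investigator believes that it is in best interest of the participant, including the following".
- **Bullets under item 3.** These include "Progressive COVID-19 requiring initiation of invasive ventilation or high flow oxygen" and, separately, an mHb level above 3%.
- **Section 7.1, item 1.** Abnormal liver tests in general are left to the Investigator. For the Hy's Law pattern the protocol says that the intervention must be discontinued.

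**The concern.** These are safety stops in an open-label, multicenter trial that Section 2.2.3 calls first-in-man. For one clinical event, a move to respiratory support above level 4, a site finds two rules in the same section. One is unconditional and covers every form of support from level 5 upward. The other depends on the Investigator's belief and names only some of those forms. NIV and high-flow oxygen share level 5, yet item 3 names one and not the other.

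A site working from the first list stops treatment. A site working from item 3 may take the stop as a matter of judgement, or take the absence of NIV as meaning that NIV is not a trigger. Treatment exposure after progression and the number of recorded discontinuations could then reflect how a site read the section as well as what happened to the patient. The Independent Data Monitoring Committee (IDMC) would be reviewing safety data collected under both readings.

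The mHb limit raises the same question of force. It is a numerical threshold for a risk named in Table 2-1, but the text does not settle whether crossing it requires a stop or only invites a judgement.

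**Working it through.** The protocol gives no figure on this point, so the check is a comparison of passages.

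**Step 1. Place each event on the scale and under each rule.**

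| Event | WHO level (8.1.1) | First list, 7.1 (also 1.1, 4.1) | Second list, 7.1 |
|---|---|---|---|
| NIV | 5 | Mandatory stop (5 > 4) | Not named |
| High-flow oxygen | 5 | Mandatory stop (5 > 4) | Item 3, if the Investigator believes it right |
| Invasive ventilation | 6 | Mandatory stop (6 > 4) | Item 3, if the Investigator believes it right |
| mHb above 3% | Not on the scale | Not covered | Item 3, if the Investigator believes it right |
| Hy's Law liver pattern | Not on the scale | Not covered | Item 1, must stop |

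**Step 2. Scope.** The first three rows are the respiratory events. The first list covers all three. Item 3 covers two and splits level 5 down the middle.

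**Step 3. Force.** High-flow oxygen and invasive ventilation are unconditional stops in the first list and conditional ones in item 3. This follows from the operative text alone.

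**Step 4. Can both lists stand as written?** The second list is introduced as an addition to the first. If the first list governs, the respiratory bullet in item 3 has no work to do, because everything it names already triggers a mandatory stop. If the bullet is to have any work to do, the first list has to be read as weaker than it is written. Neither result is a sound basis for a stopping rule.

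**Step 5. mHb.** The lead-in to the second list says that treatment should be stopped. The opening of item 3 makes that depend on the Investigator's belief. The mHb limit stands under both. Item 1 shows that the protocol can separate a judgement from an obligation. Item 3 does not do so for its own numerical limit.

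**Step 6. Trace the effect to the endpoints.**
- Section 9.1 defines progression as any level above the entry level. A participant who enters at level 3 or 4 and starts NIV is at level 5 and has therefore already had the primary event. Later treatment cannot undo it.
- Section 9.3 keeps participants who stop treatment early in follow-up for the Day 14 endpoint and analyses them as randomized. This also holds for a stop because of mHb.
- What remains open to influence is exposure after progression, discontinuation counts and safety data. Ordinal-scale values after the event and Day 28 mortality could also be touched, since treatment might or might not continue.

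**The case against.** The strongest reply is that Section 7.1 gives only one answer for NIV. The first list requires a stop, the second list adds to it and removes nothing, and item 3 is merely silent on NIV. This stands. A reader might infer that the section gives opposite instructions for a participant who starts NIV, but no operative sentence tells a site to continue. That reading comes only from the amendment summary, whose stated reason for deleting NIV from the bullet is that treatment should stop only for invasive ventilation. A summary of changes is not operative text, and its reason does not even match the edited bullet, which keeps high-flow oxygen. The reply does not remove the difference in force or explain why the bullet is there.

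A reader might also see a three-way conflict over desaturation. Item 3 lists "Inability to safely continue receiving study intervention due to compromised respiratory status while off supplemental oxygen and receiving nebulized therapy". Section 6.1 says "If the participant is unable to tolerate nebulization without supplemental oxygen, nasal oxygen may be administered during nebulization". Section 7.2 says "The participant may continue with subsequent doses if the Investigator judges that the benefit / risk ratio remains positive". The documents do not support a conflict. They describe graded steps decided by the Investigator, and Table 2-1 joins them: a pause with oxygen resumed, or a permanent stop under Section 7.1, on the Investigator's assessment. All can be followed together. One small mismatch remains: on a fall in saturation, Table 6-1 allows a pause, whereas the note to Section 7.1 calls for nebulization to be discontinued at once, pointing to Section 7.2.

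On mHb, it can be said that the protocol uses stronger language where it wants an absolute stop, so item 3 is simply discretionary. That is a fair reading, but the lead-in points the other way and the protocol should say which it means.

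Finally, a reader might put a number on those affected by taking 15% of the 200 active participants: 200 × 0.15 = 30. That figure does not count participants above level 4. Since the amendment, the 15% in Section 9.2 covers progression by at least one level, including moves from level 3 to level 4. The protocol gives no rate for NIV or for desaturation off oxygen, so any narrower count would rest on invented ranges.

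**Conclusion.** The point holds as an inconsistency of scope and force within Section 7.1. The level > 4 rule is mandatory and covers NIV, high-flow oxygen and invasive ventilation. Item 3 addresses the same event, leaves out NIV and makes the stop for the other two depend on Investigator belief. The force of the mHb limit is unclear for the same structural reason.

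The size cannot be given as a number. Only participants in the active arm (200 planned) can be affected, and among them only those who move above level 4 or exceed the mHb limit while on treatment. The consequence is possible variation between sites in exposure, discontinuation counts and safety data. The Day 14 primary comparison does not depend on it, given the event definition in Section 9.1 and continued follow-up under Section 9.3.

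The conclusion rests on the operative text of Sections 1.1, 4.1, 7.1 and 8.1.1 and needs no assumed rate. It does not imply that either stopping rule is clinically right. Correction is warranted because this is a safety stop and wording alone can settle it.

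**What to change.** In the next amendment:

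1. Reconcile the respiratory-support bullet in item 3 of Section 7.1 with the level > 4 rule in Sections 7.1, 1.1 and 4.1 and with the level definitions in Section 8.1.1, so that one event has one rule with one scope.
2. State for the limits listed under item 3, including mHb, whether each is mandatory or at the Investigator's discretion. Item 1 already shows the form of words needed to separate the two.
3. As a minor clarification, align Table 6-1 with the note to Section 7.1 on what happens to a nebulization when saturation falls.

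Which rule applies in each case is for the sponsor's clinical team to decide.

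The cost is protocol wording and a memo to sites. No extra participants, procedures or endpoints are needed, and the sample size and primary analysis are unchanged.
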